9.2 Follow-up Data Analysis

The follow-up data analysis will involve the following components.

9.2.1 Repeat the analysis described in paragraphs 9.1.2, 9.1.3 and 9.1.4 above. This is necessary in order to make sure that, when baseline and follow-up data are merged, the latent variables underpinning the measurement and structural models are based on identical structure matrices and measurement scales. That is the only way of making valid comparisons between baseline and follow-up when using multi-dimensional outcome measures. This step will involve a recalibration of all latent concepts using the combined dataset since, only when these conditions are satisfied, will we be able to present robust ‘before-and-after’ comparisons of outcomes. The adjusted models of child, parent and staff outcomes will be presented graphically along with an interpretation of their meaning and implications.

9.2.2 Having established consistent and robust measurements for all multi-dimensional outcomes relating to children, parents and staff, we will present results on impact by comparing the difference between baseline and follow-up scores. Improvements in outcomes will be expressed in terms of a comparison of means, standard deviations and effect sizes. As explained earlier, the use of effect sizes is a simple way of standardising and comparing two sets of scores and allows the impact of NEYAI to be measured in a way that is comparable to other early years programmes. Table 3 is a draft of the format that will be used to present this data.

Table 3 Format for Presenting Effect Size Scores in the Final Report

Vari- able	Effect Size Score for Treatment Group (TG)												Effect Size Score for Comparison Group (CG)										
	BC	CC	CK	CN	DD	DL	FL	LD	LK	RO	TT	All	1	2	3	4	5	6	7	9	10	All	
*																							
**																							

*Denotes a statistically significant difference between treatment group and comparison group for that variable.

**Denotes a statistically significant difference between treatment group or comparison group and the GUI for that variable.

9.2.3 Examine possible pathways associated with each net impact. Using Structural Equation Modelling, analysis of the combined dataset of treatment and comparison group will estimate if there is a difference in outcomes between the two groups and whether, in turn, this is related to the interventions in any or all of the projects. Only when this has been established, will the analysis examine the association between these interventions and other independent variables, since that is how the pathways suggested in the logic model are tested against the evidence. This will involve taking one outcome measure each for children, parents and staff, and then developing a statistical model to explain the pathways by which that improved outcome came about. We will also build a statistical model which combines all three outcome measures in order to show how the well-being of children, parents and staff are inter-connected. Within these models, relationships between variables are measured by standardised regression coefficients and each coefficient measures the unique influence of each variable on the outcome, controlling for all other variables which affect that outcome. This method of analysis is capable of yielding statistically robust insights into the pathways by which change occurs in outcome variables and is increasingly regarded by researchers and statisticians as the appropriate form of analysis for this type of evaluation.

9.2.4 Describe in more detail the interventions and pathways associated with positive impacts, as identified in the models. This is important because it is unlikely that the statistical models, on their own, will contain an exhaustive account of all factors associated with statistically-significant improvements in outcomes. That is why data on the intervention delivered by each project is important (see Section 6.4 above) as well as data from evaluation of the learning community (see Section 6.7 above). Additional case-study data, collected from projects identified as having a positive impact, may also cast light on questions which cannot be addressed easily or

comprehensively within the multivariate regression analysis - such as the role of formal and informal linkages between services; or the contribution of institutional structures such as County Childcare Committees, Partnerships and Children's Services Committees. This more detailed analysis will help improve the interpretation of results but will also assist in the process of transferring knowledge about what works in a particular project to a more general context. This is in line with the request in the evaluation's terms of reference: 'to assess the replicability and sustainability of different individual service models within the Initiative'¹⁰⁵.

9.2.5 Prepare a 'stand-alone' assessment of the learning community. It is true that no part of this evaluation is 'stand-alone' and, as described in the previous paragraph, the main interest of the learning community, from the perspective of this evaluation, is whether it is associated with any measurable impacts of the initiative. At the same time, given its innovative nature, there is merit in describing it as a separate process, possibly in a separate chapter in the final report.

9.2.6 Draw conclusions and implications from the evaluation. This is the final and, in some senses, the most important part of the evaluation since it cannot be assumed that 'results speak for themselves'; results can be over-interpreted, under-interpreted or simply misinterpreted and this can undermine the entire evaluation. We have already underlined the centrality of interpretation in the overall research design above (Section 4.4) and the careful work that is required to translate research findings – specifically statistically-significant associations between variables – into a plausible understanding of how those variables may relate to each other as cause and consequence. Equally, it is important to acknowledge that while variables may co-vary, a causal sequence cannot always be established either because the temporal 'before-and-after' sequence is unknown, or the mechanism and 'agency' connecting them is not understood. Within these limitations, the evaluation will use our analysis and interpretation of the evidence to draw out the implications for action since that is the *raison d'être* of the entire initiative. These implications may well confirm what is already known about the factors associated with positive outcomes for children and their parents but this finding, in itself, may provide the motivation that is sometimes missing in order to link knowledge to action. Equally, the implications may draw attention to variables that have no measurable impact, directly or indirectly, on outcomes and this may also be useful, particularly where existing policies and practices are based on assumptions that give undue importance to these variables.

105 Request for Tender For Evaluation of National Early Years Access Initiative, 2011:9.

10. Outputs from the Evaluation

The outputs of the evaluation, including a timetable for their delivery, are summarised in Table 4.

Table 4 Delivery Dates for Core Outputs of Evaluation

Core Outputs of Evaluation	2011	2012	2013	2014
	Final Delivery Dates			
Research Protocol	Oct			
Baseline surveys of child, parent and staff		Oct		
Data Extraction on area-characteristics of projects		Jan		
Data Extraction from Growing Up in Ireland database		Dec		
Interim Report			Mar	
Follow-up surveys of child, parent and staff			Jun	
Description of project interventions			May	
Case studies of individual service models			Dec	
Monitoring and evaluation of learning community	ongoing			
Progress Reports and Updates	ongoing			
Final Report				Mar

11. Limitations of Research Protocol

It is appropriate, by way of conclusion, to indicate the main limitations of the evaluation as set out in this research protocol. Limitations denote strength as much as weakness and are an important convention in scientific research because they set out the parameters within which research findings may be held as valid. Three limitations stand out as particularly significant.

A first limitation is that the evaluation, by virtue of focusing on how NEYAI will impact on children in the ≥ 3.5 age group, does not consider the impact on younger children aged < 3.5 . The reasons for this limitation have been explained above (Section 4); they inhere essentially in the overall budget for the evaluation since, to carry out a robust evaluation of both these age-cohorts would effectively require two separate studies with separate instruments and methods of data collection. It is true that the effectiveness of early years programmes do not appear to vary according to whether they are started before or after the age of three, although programme characteristics inevitably vary with age¹⁰⁶. At the same time, there is substantial consensus among experts in the field of early childhood that some of the most significant developments in the life of a child, and adult, take place

¹⁰⁶ 'Despite oft-heard claims that earlier is better, starting education interventions before age 3 does not appear to be a major contributor to effectiveness, although health and early nutrition components may be more effective when begun earlier. The effects of many other program features, including intensity and duration, are uncertain'. (Barnett, 2011:977)

in the period from 0-3 years, such that all subsequent developments build on experiences that take place during those years¹⁰⁷. That is why, as observed in a recent edition of *Science*, ‘age 4 cannot be characterized as “early” with respect to brain development’¹⁰⁸. Our purpose in highlighting this limitation is to draw attention to the fact that the evaluation, while contributing to the evidence-base of policy and practice for ≥3.5 year olds, will not make any corresponding contribution for children in the <3.5 age group, particularly those children whose circumstances may be more conducive to ‘developmental dysfunction’ than ‘developmental competence’¹⁰⁹. It is recognised that other studies in Ireland, most notably the infant-cohort of 11,000 children in the GUI, have potential to contribute to this evidence-base and the evaluation of NEYAI cannot realistically answer all of the challenging questions about the most effective forms of early childhood care and education for all age groups. In other words, while the evaluation will contribute to our understanding of what works for children aged ≥3.5 years, it needs to be recognised that this is only part of a much larger picture which needs to inform developments in the early years sector.

A second limitation is that most of the data used in the evaluation is based on self-report by parents and staff. This is an appropriate and tried-and-tested method of data collection, particularly where it involves the use of instruments whose validity and reliability has been well-established, as here. Nevertheless these instruments are limited and cannot provide the type of insight that could come from direct observation, such as observing interactions (eg, parent-child interactions, staff-child interactions, staff-parent interactions) or the settings in which those interactions occur (such as the way the home or childcare centre is organised, equipped, decorated, etc). Numerous studies of the early years sector testify to the power of direct observation as a robust method for yielding scientific insights into the processes of care and education that could not be obtained through self-report instruments alone¹¹⁰. It is true that the evaluation of NEYAI as outlined in this research protocol will contain a substantial amount of case-study material and other narrative accounts, but these are not the same as systematic observation by observers who are trained to a high-level of inter-rater

107 For example, a recent report on early intervention in the early years observed that: ‘babies are born with 25 per cent of their brains developed, and there is then a rapid period of development so that by the age of 3 their brains are 80 per cent developed’ (Allen, 2011:xviii; see also Perry, 2006).

108 Shonkoff, 2011:983. The author adds: ‘If early childhood policy and practice focused more explicit attention on buffering young children from the neurodevelopmental consequences of toxic stress, then scientists, practitioners, and policy-makers could work together to design and test creative new interventions that combine both cognitive-linguistic stimulation with protective interactions that mitigate the harmful effects of significant adversity, beginning as early as possible and continuing throughout preschool. For this two-pronged approach to succeed, new strategies will be needed to strengthen the capacities of parents and providers of early care and education (beyond the provision of additional information and supports) to help young children cope with stress.’ (Ibid:983-983)

109 Bronfenbrenner and Morris, 2006:803.

110 Noteworthy examples include the Effective Pre-School and Primary Education Project (EPPE) (Siraj-Blatchford, 2010a) and the NICHD Study of Early Child Care and Youth Development (NICHD Early Child Care Research Network, 2006a, 2006b).

reliability¹¹¹. These types of observation are expensive and time-consuming, reflected in the fact that a just-completed, and outstanding, doctorate in early childhood education in Ireland was based on the direct observation of just three staff engaged in six ‘small group learning experiences’¹¹². That is why, in effect, this methodology is not appropriate to the scale of NEYAI and its budget for evaluation. This limitation implies that certain aspects of care and education provided through NEYAI projects will not be evaluated – or at least not in the detail that would be possible through direct observation – such as the pedagogical skills of staff¹¹³ or the interaction styles with parents¹¹⁴.

A third limitation is that the evaluation cannot assess if NEYAI impacts, where identified, are sustainable. As with the other limitations, there are budgetary reasons for this. The research protocol is based on a simple ‘before-and-after’ design with a comparison group and there is no provision to follow-up children, parents or staff to see what benefits of NEYAI might be evident, other things being equal, in 1, 2, 3, 5 or even 10 years after the intervention. Many of the studies which have left a lasting legacy on the early years sector have involved waves of data collection and analysis over many years¹¹⁵. In general, these studies suggest that all effects tend to diminish over time; however larger effects (such as effect sizes in the region of 0.3 for programmes like High Scope) tend to last for many years while smaller effects (such as effect sizes below 0.2 for programmes like Head Start and Early Head Start) tend to disappear within a year or two¹¹⁶. This

111 Inter-rater reliability has been defined as ‘The degree of agreement among people collecting data or making observations on what they decide when collecting the same data from the same data sources for the same cases using the same directions. It is measured as the percentage of agreement when either:

- Several people collect data from the same sources for the same cases, or
- One person collects data from the same sources for the same cases at different times.’ (Dixon and Pearce, 2010:18).

112 French, 2011.

113 It is well-established that the pedagogical skills of childcare staff have a significant influence on a wide range of child outcomes (Pianta, Barnett, Burchinal and Thornburg, 2009). In broad terms, these skills vary along a continuum from ‘adult-directed’ to ‘child-directed’. Studies confirm that cognitive gains are associated with both ‘adult-directed’ learning (Barnett, 2011:977) and ‘child-directed’ learning (Siraj-Blatchford, 2010a:157) while gains in socio-emotional development and executive function are likely to require a balance of both.

114 Parent-child interactions are recognised as foundational to human development: ‘Especially in its early phases, but also throughout the life course, human development takes place through ... interaction To be effective, the interaction must occur on a fairly regular basis over extended periods of time’ (Bronfenbrenner and Morris, 2006:797). These interactions are heavily influenced by the sensitivity of the adult, particularly the mother, and involve acceptance, responsiveness and warmth towards the child (Whittaker, Jones, See, Meisch and Westbrook, 2011:83-84).

115 The outstanding example of this is High Scope which was first introduced into Perry Elementary School in the Michigan city of Ypsilanti in 1960 and has tracked children from age 3 to 40 (Schweinhart, Montie, Xiang, Barnett, Belfield and Nores, 2005; Heckman, Moon, Pinto, Savelyev and Yavitz, 2009).

116 Barnett, 2011:976; see also Camilli, Vargas, Ryan and Barnett, 2010; Nores and Barnett, 2009. Some measures recommended to improve the effect size of Early Head Start (EHS) and Head Start (HS) also draw attention to the active ingredients in early years programmes: ‘EHS and HS might improve their results by providing richer educational experiences. EHS could increase and improve both parenting education and direct classroom experiences. HS may need to focus more resources on the classroom to recruit and retain better teachers. Improving teaching practices may also require increased spending on supervision and

suggests that the size of the initial effect may provide an early indication as to its sustainability. Nevertheless, this limitation needs to be kept in mind since the sustainability of NEYAI impacts, where identified, can only be assumed rather than proven.

As indicated, the acknowledgement of limitations is an important convention in scientific research whose purpose is to protect against over-interpretation or under-interpretation of results and their implications. That is why the limitations just discussed do not detract from the fact that the evaluation, as proposed, will answer robustly the two core questions that it was designed to address:

- (i) Does NEYAI have an impact on children and their parents by comparison with a 'matched' sample of those who have not participated in NEYAI?
- (ii) If NEYAI has an impact, how does this come about, for whom, in which projects, using what type of intervention(s), etc?

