50 Traditionally, it has been common for researchers, using regression analysis, to treat all variability in an outcome as attributable to individual-level variation (level 1), and to assume that each individual-level observation is independent and not influenced by the setting which individuals may share such as the same neighbourhood, school, hospital, programme, etc (level 2). The effect of this is to over-estimate individual-level influences, where they occur, and to overlook group-level influences which are properly attributable to setting. When these two sources of variability are not separated in statistical analysis, and only sources of variation at level 1 are considered, there is a danger that the influence of predictor variables may be over-estimated since sources of variation at level 2, where they occur, are assumed to occur at level 1 only; correspondingly, there is an under-estimation of the variability that is random or unexplained, usually referred to as ‘the error variance’. Multi-level modelling was invented to overcome these problems which are not just ‘statistical’ problems but have practical consequences. The practical consequence of this is that, when drawing out practice or policy implications of analysis, one may place too much importance on individual-level predictors or, conversely too little on how these individual-level predictors may vary in their influence from one setting to another.

the interpretation. Within confirmatory programme evaluation⁵¹, and in other fields of inquiry where causal inference is required such as epidemiology⁵², these criteria typically include the following:

1. Temporality

This is generally regarded as the most basic criterion of causal inference since a cause must precede its effect in time. That is why the research design for this evaluation is based upon a 'before-and after' comparison of those who participate in NEYAI with those who do not.

2. Size & Strength

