102 'Any effects discerned in the evaluation have to be considered "putative" because the data for the NESS and MCS samples of 5-year olds and their families were collected two years apart and by two different research teams. This makes attributing any discerned SSLP effects to SSLP exposure per se difficult, as they could potentially reflect changes taking place in communities or society more generally across the two-year period in question or be the result of differences in approaches to measurement by the two research teams, although close cooperation did occur with respect to staff training. Indeed, possible time of measurement effects were identified in the NESS Impact Study when children were 3 years old with respect to child immunisations. That is, apparently positive effects of SSLPs on immunisations were found to be possibly a function of the time difference between when NESS and MCS 3-year old data were collected rather than an effect of SSLPs on immunisations' (National Evaluation of Sure Start Team, 2010:iv).

timeframe for data collection will be agreed with each project within the parameters that all baseline data will be collected by the end of October 2012 and all follow-up data will be collected by the end of June 2013.

There are fewer constraints on data collection for the comparison group but the timeframe will broadly mirror that of the treatment group. As indicated above, further work is required, in collaboration with Pobal, to support data-collection for the comparison group, possibly through the County Childcare Committees or Partnerships or both.

8. Ethical Considerations

The main ethical and legal requirement in the study is to ensure that the right of children, parents and staff to privacy and confidentiality is respected at all times. This right is enshrined in the Data Protection Acts 1988 and 2003.

Bearing this in mind, the consent of each parent is required to allow childcare staff assess each child using the Child Questionnaire. Similarly, the consent of each parent is required before any contact details can be passed over to the evaluation team in order to carry out the interview using the Parent Questionnaire.

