Communication and language	0.03	-0.08 to 0.14	0.61	0.03
Problem-solving, reasoning, numeracy	0.04	-0.07 to 0.15	0.49	0.04
Knowledge/ understanding of the world	-0.02	-0.13 to 0.09	0.70	0.02
Physical development	-0.05	-0.16 to 0.05	0.33	0.05
Creative development	0.00	-0.12 to 0.11	0.99	0.00
Foundation profile score total	0.01	-0.09 to 0.11	0.83	0.01
Maternal Wellbeing				
Mother's satisfaction with life	0.21	0.08 to 0.33	0.00	0.10
Mother's rating of safety in area	0.03	-0.03 to 0.10	0.27	0.03
Mother's self rated depression	0.40	0.14 to 0.65	0.00	0.09
Parent and Family Functioning				
Harsh discipline in home	-0.13	-0.18 to -0.08	0.00	0.24
Chaos in home	-0.24	-0.36 to -0.13	0.00	0.29
Home learning environment	0.17	0.09 to 0.24	0.00	0.27
	Odds ratio	95% CI	p	
Parents attended school meetings	- 0.43	-0.34 to- 0.56	0.00	

(i) Effects are adjusted for child, family and area characteristics and strata.

(ii) The mean effect size across all three sets of analyses for those outcomes which were significantly related to SSLP status across all three sets of analyses.

CI=Confidence interval

Results in bold italics are replicated as statistically significant across all 3 data sets.

Source: National Evaluation of Sure Start Team, 2010:29.

Guidelines for Project Coordinators to Support the Evaluation

1. Coordinators are the link between the childcare centres and the Evaluation Team. As such, they have a key role to play in ensuring that the evaluation is carried out as planned and agreed. The core of the evaluation is based on data collected using three questionnaires: Staff Questionnaire, Child Questionnaire, and Parent Questionnaire. These questionnaires are completed at baseline (at a time to be agreed with each project but always **before** any intervention begins but not later than October 2012) and at follow-up (again, at a time to be agreed with each project but not later than June 2013). Coordinators have a particularly central role in data-collection using the Staff Questionnaire and the Child Questionnaire as well as keeping an accurate record of the intervention which is being implemented in their project. The Parent Questionnaire will be administered by an independent team of interviewers.

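### With parents, staff and children all measured only at the same two waves, the pathway models in Section 9.2.3 cannot tell a parent or staff pathway from spillover of a child effect, yet the protocol promises a robust answer on how NEYAI works

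*Protocol*

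**What the plan says.** **Design.** Appendix Two states that "The core of the evaluation is based on data collected using three questionnaires: Staff Questionnaire, Child Questionnaire, and Parent Questionnaire", and that these are completed at baseline and at follow-up. Section 7 sets baseline collection by the end of October 2012 and says that "all follow-up data will be collected by the end of June 2013". Section 11 describes a "design with a comparison group and there is no provision to follow-up children, parents or staff" in later years, comparing before and after only. No parent or staff measure is placed between the two waves.

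**Pathway analysis.** Under Section 9.2.3, the interventions are related to the remaining variables only after a net impact has been shown. The reason given is "since that is how the pathways suggested in the logic model are tested against the evidence". That step covers the link from programme to pathway variable. The link from pathway variable to outcome comes later in the same paragraph, where each standardised coefficient is read as the separate influence of a variable on the outcome. The paragraph adds: "This method of analysis is capable of yielding statistically robust insights into the pathways by which change occurs in outcome variables". It names no lag and no reverse path.

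**Causal standard.** Section 4.4 lists temporality first among its criteria because "a cause must precede its effect in time", and offers the before-and-after comparison of participants and non-participants as the reason for the design. Step 5 in Section 4.2 makes the pathway step a test of hypothesised causal mechanisms.

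**Caveats.** Section 4.4 says that statistical association does not by itself show cause. Section 9.2.6 concedes that "a causal sequence cannot always be established either because the temporal 'before-and-after' sequence is unknown". Section 11 lists three limitations: the age group, self-report, and no long-term follow-up. It then says that both core questions will be answered robustly.

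**The concern.** The logic model says that NEYAI changes parents and staff, and that this change then improves the child. The before-and-after design meets the temporality criterion for programme to outcome. It does not meet it for pathway variable to outcome, because both are scored at the same two points.

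Suppose the programme acts directly on the child, and a child who is doing better lifts the mother's well-being. At follow-up the programme group then has better parent scores, and parent and child scores are correlated within groups. A true parent pathway leaves the same two traces.

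Core question (ii) asks how any impact comes about. If the direction is read from these coefficients, advice to target parents or staff could rest on a consequence of the child effect and not on its cause.

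**Working it through.** **1. The plan's own figures.** 35 × 11 = 385 per group, and 2 × 385 = 770. For an effect of 0.2 SD (two-sided 5%, power 80%, no clustering), n = 2(1.96 + 0.84)²/0.2² ≈ 393 per group, so 385 is consistent. These figures are not in dispute.

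**2. A world with no parent pathway.** From the protocol: 385 per group, and child effects d of 0.2 to 0.5 SD (Section 5). Assumed: wave-to-wave stability 0.6, baseline child-parent correlation 0.3, no clustering, and spillover g from child change to parent. One value of g is 0.46, the coefficient under Figure 2. There it runs from parent to child; reversing it is an assumption.

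- Child: C₁ = 0.6·C₀ + d·T + e
- Parent: P₁ = 0.6·P₀ + g·(d·T + e) + u
- e and u have variance 1 − 0.6² = 0.64, so SD 0.8. The parent has no effect on the child.

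A parent pathway is counted when two coefficients are significant, each adjusted for both baselines: programme to parent, and parent to child given programme. This joint rule is a device for illustration; the protocol does not state it.

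**3. Probability of a false parent pathway.**

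- Programme to parent: expected coefficient g·d, standard error 0.8·√(1 + g²)·√(2/385), with √(2/385) = 0.0721.
- Parent to child: the true effect is zero, but the expected test statistic is about g·√770. At g = 0.1 this is 2.77 (significant with probability 0.79). At g = 0.2 it is 5.55 (practically certain).

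| d | g | g·d | SE | z | first link significant | both, by formula | both, by simulation |
|---|---|---|---|---|---|---|---|
| 0.3 | 0.1 | 0.030 | 0.0579 | 0.52 | 0.08 | 6% | 7% |
| 0.3 | 0.2 | 0.060 | 0.0588 | 1.02 | 0.175 | 17.5% | 17% |
| 0.3 | 0.3 | 0.090 | 0.0602 | 1.50 | 0.32 | 32% | 34% |
| 0.3 | 0.46 | 0.138 | 0.0635 | 2.17 | 0.585 | 59% | 59% |
| 0.2 | 0.46 | 0.092 | 0.0635 | 1.45 | 0.305 | 31% | 32% |
| 0.5 | 0.46 | 0.230 | 0.0635 | 3.62 | 0.95 | 95% | 95% |

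Formula and simulation agree to within about two percentage points. With no child-parent link the rate is about 0.2%. At 330 per group (30 × 11, after the planned drop-out), with spillover 0.3 or 0.5 and child effects of 0.2 to 0.5, it runs from 14% to 95%.

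**4. Would a lagged path settle the direction?** Only in part. In the same false-pathway world, a test that uses the baseline parent score stays near its nominal 5%. But baseline is taken before the intervention, so that score contains no programme-induced change. Where the programme truly changes the parent and that change moves the child with coefficient 0.46, a rule requiring the lagged path finds the pathway in only 4% to 5% of runs, against 93% to 100% for the same-wave path. If the parent's level drives the child, the two do equally well (92% each at an effect of 0.2). With score reliability 0.8 and baseline correlation 0.3, the lagged rule falsely passes in 4% to 12% of runs.

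**The case against.** The strongest reply is that Section 9.2.3 fixes very little. It names no same-wave path, no significance rule and no timing for the pathway variable. Lagged, change-score or non-recursive models all remain open, and an analysis plan may choose among them. A reader might infer that the protocol plans a concurrent joint-significance test, but the text does not say so. What stands regardless is the design: two waves, with no pathway measure between them. No choice of model supplies the missing order.

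A reader might also infer that the protocol would declare a reversed pathway confirmed, in breach of its own temporality rule. The documents do not support that. Section 4.4 refuses to infer cause from association and applies six criteria. Sections 4.4 and 9.2.4 add qualitative and case-study evidence, and Section 9.2.6 admits that the order may be unknown. These caveats are real but general. None says how a path of unknown direction will be reported, and they sit beside two unqualified assurances of robustness.

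The size is open to challenge too. It depends heavily on the spillover, which is unknown. Figure 2 comes from a pooled sample that the protocol says is not nationally representative. The child's main instrument is completed by staff, while the mother is interviewed, so strong spillover across informants is not established. Staff are trained or mentored directly in most projects, and the parent figures cannot simply be carried over to them.

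**Conclusion.** The point holds as a limit on what the pathway analysis can show. With pathway variables and outcomes measured only at the same two waves, the coefficients in Section 9.2.3 cannot separate a parent or staff pathway from spillover of a child effect. The robustness claims in Sections 9.2.3 and 11 go further than the design allows for question (ii), and Section 11 does not list this limitation.

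The size is illustrative. It may be slight (about 7% at spillover 0.1 for a 0.3 SD effect) or large (32% to 95% at spillover 0.46 for effects of 0.2 to 0.5 SD). It rests on the assumed stability, baseline correlation, absence of clustering and joint-significance rule. For staff the same argument about timing applies, but no rate was computed. The finding does not touch question (i), whether NEYAI has an impact.

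**What to change.** In Section 9.2.3:

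- State that parent-child and staff-child paths estimated within the same wave are reported as associations of undetermined direction.
- Report the programme effect on each pathway variable, adjusted for baseline.
- Fit two further paths as sensitivity analyses: baseline pathway variable to follow-up outcome given baseline outcome, and the reverse, baseline outcome to follow-up pathway variable. Do not make either a pass/fail condition, since step 4 of the working shows that such a condition can miss real pathways.

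In Section 11, add the ordering of pathway variables to the limitations, and qualify the closing assurance for question (ii).

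The cost is a little more analysis on data already planned, and a less favourable statement of what the pathway models show.
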